subjects received the assigned fixed dose of USVCAP further for 12 weeks (Table 2). Therefore, the overall duration of treatment with USVCAP for subjects in Groups B and C was 13 and 14 weeks, respectively

- End-of-treatment: The end-of-treatment (EOT) for each randomized subject was defined as Day when 12-weeks of twice daily administration of assigned fixed dose of IP was completed by a subject (Table 2 and Table 3)
- Visit 7 was the EOT visit: It was conducted on next day after the subject had completed twice daily administration of assigned fixed dose of IP for 12 weeks (Table 2)
- Post-treatment safety follow-up period: It was of 4-weeks duration after the subject had completed administration of the last dose of assigned fixed dose of IP. Visit 8 was the end-of-study (EOS) Visit in the study.

The Investigator followed the schedule of study assessments and procedures provided in Table 2. A window period of +2 days was allowed at every visit from Visit 3 to Visit 8 and at Visit DE 1 and Visit DE 2.

Pre-study oral anti-diabetic treatment (i.e. monotherapy with metformin hydrochloride) was continued at same dose and regimen from screening up to EOT period. A subject diary was provided to the subjects for recording the IP dosage, capillary glucose measurements, AEs, details on hypoglycaemic episodes, and any change in concomitant medications, as applicable.

The following Standard of Care was provided to each subject throughout the treatment period:

- 1. Step-wise dose escalation in subjects assigned to receive higher doses of USVCAP (i.e. subjects assigned to received fixed dose of 150 IU and 300 IU, BD)
- 2. Pre-study oral anti-diabetic monotherapy (i.e. metformin hydrochloride) continued at same dose and regimen
- 3. Capillary glucose measurements
- 4. Consumption and maintenance of healthy diet and lifestyle regimen
- 5. Treatment for complications related to insulin therapy (e.g. hypoglycaemia, hypokalaemia, etc.) or any other complications as per Investigator's practice and standard treatment guidelines

The Schedule of Study Procedures and Assessments is given in Table 3.

Table 1	Duration	of	Run	in	period(s)	and	treatment	for	doses	of	IP	per	each	Allocated
Treatmo	ent Group													

Treatment Group	Assigned fixed dose of	Treatment duration with assigned fixed	Run-in period/s with lower dose/s of USVCAP	Overall total duration of treatment with			
	USVCAP	dose of USVCAP		USVCAP			
Group A	75 IU BD	12 weeks	Not applicable	12 weeks			

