The screening procedure and assessments started only after signing of the ICFs. A subject was enrolled within 21 days of performing procedures/investigations for screening. Upon obtaining the informed consent, the subjects were allocated a unique subject identification (Subject ID) number and were screened to confirm the eligibility for participating in this study. Subjects who fulfilled the eligibility criteria were randomized in the study, while subjects who did not fulfilled the eligibility criteria were termed as 'screen failures'

The screening procedures and assessments were conducted as described below:

- Informed consent procedure: Written and signed informed consent were obtained from all subjects prior to conduct of any study procedures.
- Inclusion and exclusion criteria were checked
- Recording of medical/surgical history including relevant details related to T2DM
 - Date of diagnosis of T2DM. If complete date was not available, the year and month was recorded. If month was not available, at least year of diagnosis was recorded
 - History of alcohol dependency/drug abuse and/or was a current alcohol/drug abuse dependent
 - History of smoking or tobacco chewing and/or was a current smoker/tobacco user
- Recording of prior medication history (including current anti-diabetic medication, previous anti-diabetic therapy within 3 months prior to enrolment)
- Collection of demographic information, including height (cm)
- Recording of findings from physical examination
 - $\circ~$ Recording of body weight (kg), waist circumference (cm) and body mass index (BMI) (kg/m²)
 - Recording of vital signs: Systolic BP (SBP) and diastolic BP (DBP) (mm/Hg), pulse rate (PR) [beats/min], respiratory rate (RR) [breaths/min] in supine position after 5 minutes of rest and body temperature (degree Fahrenheit[°F])
- Laboratory investigations:
 - Blood samples were withdrawn from the subject to conduct the following laboratory investigations at a central laboratory:
 - Fasting Plasma Glucose
 - Postprandial plasma glucose (2-hours after meal)
 - HbA1c
 - Haematology: Red blood cells (RBCs) count, haemoglobin (Hb), platelet count, white blood cells (WBCs) count including differential count
 - Lipid profile: Total cholesterol, high density lipoprotein (HDL), low density lipoprotein (LDL), very low density lipoprotein (VLDL), and triglycerides after 12 hours of fasting

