 - Liver function tests: Alanine aminotransferase (ALT), aspartate aminotransferase (AST), Alkaline phosphatase (ALP), and total bilirubin

- Renal function tests: Serum creatinine, blood urea nitrogen (BUN), sodium, potassium, chloride, and estimated glomerular filtration rate (eGFR)
- Total protein & Albumin to globulin ratio (A/G ratio)
- Calcium, phosphorus, vitamin D, Parathyroid hormone (PTH)
- Serology tests: human immunodeficiency virus (HIV), hepatitis B virus (HBV), and hepatitis C virus (HCV) tests
- Insulin Antibody test- Anti insulin antibody test
- Urine samples were collected for:
 - Urine pregnancy test (UPT): Only for female subject of childbearing potential or who are ≤ 1 year postmenopausal prior to enrolment
 - Urinalysis: routine examination
- Recording of 12 Lead electrocardiogram recording (ECG)
- Recording of AE/ serious adverse events (SAEs), if any
- Recording of concomitant medications, if any

Visit 2 (Baseline Visit/ Randomization/ Enrolment Visit)

The following procedures and assessments were performed at this visit:

- Review of inclusion and exclusion criteria obtained during screening procedures and assessments
- Review of medical and surgical history recorded at Visit 1
- The following details were recorded at this visit:
 - Findings of physical examination
 - $\circ~$ Body weight (kg) and waist circumference (cm) and body mass index (BMI) (kg/m^2)
 - Vital signs: SBP and DBP (mmHg), PR (beats/min), RR (breaths/min) after 5 minutes of rest and body temperature (degree Fahrenheit [°F]) in supine position
 - AE/SAE, if any
 - Prior and concomitant medications, if any
- Training to perform capillary glucose measurements. (Appendix 16.1.13 for detail).
- Subject randomization using IWRS (prior to dispensing of 1st dose of IP)
- Dispensing of IP: The subjects were dispensed IP doses during the treatment period (including the run-in period) as per the dose required per allocated treatment groups (Group A, Group B or Group C).
 - At this visit only: All subjects randomised to Group A, B, and C were dispensed USVCAP capsules of dose strength 75 IU
 - Subjects randomised to Group A were prescribed 1 capsule of USVCAP (i.e. assigned fixed dose 75 IU, BD for 12 weeks) from next day (i.e. Day 1) after randomisation. They were instructed to visit the study site for their next scheduled visit (Visit 3 [Day 8 [+2 days])

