The safety of USVCAP formulation in Type 2 Diabetes Mellitus Subjects Uncontrolled with Metformin Hydrochloride Treatment was determined by incidence and severity of treatment emergent adverse events (TEAEs) that occurred during the study period, including occurrence of hypoglycaemic episodes in each treatment group during the study period; and change in laboratory investigations post 12-week administration of USVCAP. Efficacy of the treatment was assessed by change in glycated haemoglobin (HbA1c) level post 12-week twice daily administration of selected fixed dose of USVCAP (75 IU, or 150 IU or 300 IU) from baseline, comparison of change in HbA1c between the 3 fixed dose levels studied to examine dose response relationship post 12-week administration of USVCAP and change in FPG and 2-hour PPG levels in each treatment group post 12-week administration of USVCAP. The immunogenicity was assessed by evaluating incidence of treatment-emergent antibody response (TEAR).

Selection of Study Population

Inclusion Criteria

- 1. Male or female aged 35 to 60 years (both inclusive)
- 2. Type 2 diabetes mellitus diagnosed < 2 years prior to enrolment
- 3. Glycated haemoglobin level $\ge 7\%$ and $\le 9.5\%$
- 4. On stable oral monotherapy with metformin hydrochloride (1000 mg to 2500 mg/day) and regular diet and exercise regimen at least 12 weeks prior to enrolment
- 5. Body mass index between 18 to 30 kg/m2
- 6. Ability to perform capillary blood glucose measurements

- 7. Willing to provide informed and written consent for the clinical trial
- 8. Able to comply with all requirements of clinical trial protocol

Exclusion Criteria

- 1. Subject with history or evidence of hypersensitivity to insulin or metformin hydrochloride or its excipients
- 2. Suffering from type 1 diabetes mellitus
- 3. Received treatment with sulphonylureas or alphaglucosidase inhibitors, Glucagon-like peptide-1 (GLP-1) receptor agonists or Sodium-glucose co-transporter 2 (SGLT2) inhibitors or meglitinides or pramlintide or thiazolidinediones within 3 months prior to enrolment
- 4. Previously treated with insulin within 3 months prior to enrolment
- 5. History of episodes of hypoglycaemia during 3 months prior to enrolment.
- 6. Reduced awareness of hypoglycaemia or inability to identify and tackle hypoglycaemic episodes
- 7. History of substantial weight loss defined as 5% decrease in body weight within the last 6 months
- 8. Medical history of unstable angina within 1 year prior to enrolment

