- 9. History of tobacco or nicotine more than two packs/day within 3 months prior to enrolment
- 10. Is, at the time of signing informed consent, a user of recreational or illicit drugs or has had a recent history (within 1 year prior to enrolment) of drug or alcohol abuse or dependence. (Note: Alcohol abuse includes heavy alcohol intake as defined by >3 drinks per day or >14 drinks per week, or binge drinking).
- 11. History of gastrointestinal disorders which may potentially interfere with absorption of the IP
- 12. Treatment with systemic corticosteroids or with inhalational corticosteroids (Beclomethasone or budesonide) within the 3 months prior to enrolment
- 13. Likelihood of requiring treatment during the study period with prohibited medications mentioned (as defined in this clinical trial protocol)
- 14. Female subject who is pregnant, lactating or planning pregnancy during the trial
- 15. Female subject of childbearing age who is not willing to use adequate method of contraception during the study period
- 16. Life expectancy of less than 6 months from screening
- 17. Elective surgery or any other surgical procedure/s requiring general anaesthesia during the clinical trial
- 18. Has participated in another research trial within 12 weeks prior to screening
- 19. History of diabetic ketoacidosis requiring hospitalization within 6 months prior toenrolment, case of proliferative retinopathy or advanced neuropathy
- 20. Subject having any of the following laboratory results at screening
 - a. Estimated glomerular filtration rate (eGFR) <45 mL/min/1.73 m²

- b. Alanine aminotransferase (ALT) and/or Aspartate aminotransferase (AST) >3 times of upper limit normal
- c. Blood urea nitrogen (BUN) > 30 mg/dL
- 21. Subject who has a positive serology for hepatitis B virus (HBV) or hepatitis C (HCV) or human immunodeficiency virus (HIV) infections at screening
- 22. Subject who has undergone pancreatectomy or pancreas islet transplant or renal transplant
- 23. Subject receiving or has received any immunomodulation medications within 1 year prior to enrolment
- 24. Subject with history or evidence of diabetic complications (e.g. diabetic retinopathy, diabetic neuropathy, or diabetic nephropathy, etc.), cardiac disorders, or any other systemic complication due to diabetes, which in the opinion of the Investigator signifies subjects' ineligibility for the trial

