The efficacy assessments HbA1c, FPG and 2-hour PPG were assessed at the central laboratory identified for the study.

It was performed as follows:

- At screening to confirm the eligibility of the subject in the study
- During the treatment period and at EOT to evaluate to assess the safety and the treatment response
- At the EOS to evaluate the post-treatment safety of the subjects after twice daily administration of IP for 12 weeks

The blood samples for HbA1c, FPG and 2-hour PPG were withdrawn from the subject for the following tests:

- Glycated haemoglobin at Visit 1 and Visit 7
- Fasting plasma glucose level under fasting condition i.e. at least 8–10 hours of overnight fasting at Visits 1, 3, 4, 6, and 7 for all subjects

For Group B subjects: Prior to Visit DE 1

For Group C subjects: Prior to Visit DE 1 and Visit DE 2

• Postprandial glucose level (2-hours after meal) at Visits 1, 3, 4, 6 and 7 for all subjects. For Group B subjects: Prior to Visit DE 1

For Group C subjects: Prior to Visit DE 1 and Visit DE 2

• All samples were sent to central laboratory for evaluation. FPG and 2-hour PPG test results at Visit DE 1 and Visit DE 2 should be available prior to dosing.

Capillary glucose measurements

Capillary glucose measurements were performed by the subjects using a self-monitoring blood glucose device throughout the treatment period (from Visit 2 to Visit 7), once every week (mid-week).

During run-in period(s) (from Visit 2 to DE 1 [in Group B subjects] and from Visit 2 to Visit DE 1 and from Visit DE 1 to Visit DE 2 [in Group C] subjects), capillary glucose measurements were performed at mid-week.

The capillary glucose measurements were performed at the following 4 time points:

- Fasting: After 8 hours of overnight fast
- 2-hours post-breakfast
- 2-hours post-lunch
- 2-hours post-dinner

The measurements for all 4 timepoints were performed on the same day. All capillary glucose measurements were recorded by subject in the respective visit subject diary.

Hypoglycemia

It was important for subjects in the study to recognize signs and symptoms of hypoglycemia. Subjects enrolled in the study were educated on signs and symptoms of hypoglycemia and were instructed to keep glucose tablets handy & take 4 glucose tablets (total 15 -20 grams of glucose) immediately to treat hypoglycemia, if it occurs.

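### Stability and washout periods are counted back from enrolment, but the baseline HbA1c is drawn up to 21 days earlier; a minor, cheaply fixed source of drift in the uncontrolled primary test

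*Combined protocol and SAP*

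**What the plan says.** **Anchor.** Inclusion Criteria, item 4, requires stable metformin monotherapy with "regular diet and exercise regimen at least 12 weeks prior to enrolment". Exclusion Criteria, item 4, removes subjects "Previously treated with insulin within 3 months prior to enrolment"; item 3 uses the same anchor for other glucose-lowering drugs. Item 12 reads "Treatment with systemic corticosteroids or with inhalational corticosteroids (Beclomethasone or budesonide) within the 3 months prior to enrolment".

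**Which visit is enrolment.** The visit description is headed "Visit 2 (Baseline Visit/ Randomization/ Enrolment Visit", and Table 2 places it at Day 0. Under Visit 1 the plan states: "A subject was enrolled within 21 days of performing procedures/investigations for screening". Enrolment therefore cannot mean screening. Exclusion 18 counts back from screening instead, so the plan treats the two dates as different anchors.

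**When HbA1c is measured.** Efficacy Assessment lists "Glycated haemoglobin at Visit 1 and Visit 7", and Table 2 agrees. None is drawn at Visit 2, although that visit carries the baseline label. The change from baseline in Primary Analysis must therefore use the Visit 1 value.

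**What might close the gap.** Metformin "was continued at same dose and regimen from screening up to EOT period", which fixes the dose only from Visit 1 onward. The eligibility review at Visit 2 applies the same enrolment anchor. Inclusion 2 reads "Type 2 diabetes mellitus diagnosed < 2 years prior to enrolment", which sets no minimum duration.

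**Analysis.** The primary test is a paired t-test on HbA1c within each dose group. All three groups receive the drug.

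**The concern.** A 12-week stability rule exists so that the baseline HbA1c reflects settled treatment. That works only if the 12 weeks end when the blood is drawn. Here they may end up to three weeks after it.

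A subject who started metformin, or settled into diet and exercise, exactly 12 weeks before Visit 2 can have the baseline sample taken at week 9, while HbA1c is still falling. The rest of that fall then appears in the Visit 7 change. The same sample decides whether the subject counts as uncontrolled on metformin.

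A recently stopped steroid works in the same direction. A recently stopped glucose-lowering drug or insulin works in the opposite one: HbA1c may still be rising, which would mask drug effect.

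The primary comparison has no untreated arm, so nothing in it separates this drift from drug effect.

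**Working it through.** **1. The plan's yardstick.** Determination of Sample Size assumes a 0.5-point fall and an effect size of 0.5 (hence an SD of the change of 1.0), two-sided alpha 2.5% and 90% power, giving 52 per group. The normal approximation gives 50 and the exact noncentral t gives 53; n = 52 has 89.9% power. The figure of 52 is reproduced to within 2 subjects, so 0.5 points and an SD of 1.0 are the scale for what follows.

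**2. Timing, from the documents alone.**
- Metformin, diet and exercise: 12 × 7 − 21 = 84 − 21 = 63 days = 9 weeks.
- Three-month washouts: 90 to 92 days − 21 = 69 to 71 days, about 10 weeks.
- Counted back from the Visit 1 sample, the first figure would be 84 days.

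**3. Residual drift, on assumptions.** The documents give no HbA1c kinetics. Assume HbA1c is a weighted average over a 120-day red-cell life with linearly falling weights. The share still reflecting the period before a change made t days earlier is (1 − t/120)².
- t = 63: (57/120)² = 0.226
- t = 84: (36/120)² = 0.090
- Part due to the anchor: 0.226 − 0.090 = 0.136

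In this worst case Visit 7 (Day 85 in Group A, later in B and C) falls at least 84 + 85 = 169 days after metformin start. That exceeds 120 days, so the whole remainder lies inside the measured change.

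For an assumed 1.0-point metformin effect, the anchor costs at most 0.136 points in one subject, or 0.136/0.5 = 27% of the planned reduction. For assumed effects of 0.5 and 1.5 points it is 0.068 and 0.203.

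**4. Screening gaps shorter than 21 days.** If gaps are spread evenly over 0-21 days (assumed), the average residual share is (40/21) × (0.475³ − 0.300³) = 0.153. The anchor's part is 0.153 − 0.090 = 0.063.

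**5. Group mean.** Multiply by an assumed 10% or 30% of subjects who started exactly 12 weeks before enrolment, at a 1.0-point effect:

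| Screening gap | 10% | 30% |
|---|---|---|
| Full 21 days for all | 0.014 | 0.041 |
| Even over 0-21 days | 0.006 | 0.019 |

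Varying the effect from 0.5 to 1.5 points widens this range to 0.003-0.061.

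**6. A second model.** Assume instead an exponential approach to steady state, with a half-life of 3 to 5 weeks and an effect of 0.5 to 1.5 points. For one subject in Group A with the full 21-day gap:

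| Case | 9 weeks before sample | 12 weeks before sample | Difference |
|---|---|---|---|
| Low (3 weeks, 0.5) | 0.061 | 0.030 | 0.031 |
| Mid (4 weeks, 1.0) | 0.195 | 0.116 | 0.079 |
| High (5 weeks, 1.5) | 0.378 | 0.249 | 0.129 |

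With 30% of the group at the minimum and no drug effect, the false-positive rate (n = 52, SD 1.0, two-sided 2.5%) is 3.8% as written against 2.9% re-anchored in the mid case, and 7.6% against 4.6% in the high case.

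**7. Between doses.** Group C reaches Visit 7 two weeks later than Group A. In the mid case the drift is 0.199 in C against 0.195 in A, a difference of 0.004.

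**The case against.** **Worst case, not typical.** Twenty-one days is the maximum gap and 12 weeks the minimum stable period. A reader might infer that subjects in general had only 9 stable weeks. The documents do not support that; they give neither the actual screening gaps nor the share of recent starters. This stands, and is why the group-mean figures matter more than the single-subject one.

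**Total drift is not the anchor's drift.** A reader might take the full 0.226 points, 45% of the planned 0.5, as the cost of the anchor. The same model leaves 0.090 at 12 weeks, which re-anchoring would not remove. Only 0.136 belongs to the anchor.

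**The criterion says stable.** Someone whose dose was titrated began metformin before the stable period, and part of the effect may already have passed. The extreme case needs an immediate, unchanged, qualifying dose. This too lowers the likely size.

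**Direction.** A reader might infer that all the drift is credited to the drug. That fails for exclusions 3 and 4, where it would hide effect.

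**The real weakness is the uncontrolled test.** True: any pre-existing trend passes through it. But the stability rule is the design's own protection against such a trend, and the anchor shortens it by up to a quarter (21 of 84 days).

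**Conclusion.** The point holds as a minor one. The timing follows from the text alone: as little as 9 weeks of stable metformin, or about 10 weeks of washout, before the baseline HbA1c. No other provision closes the gap.

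The size rests on assumed kinetics, an assumed metformin effect and an assumed share of recent starters. With a 1.0-point effect and a 10-30% share, the anchor shifts the group mean by about 0.01-0.04 points, small against the planned 0.5. The washout criteria were not sized separately.

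The exposed analysis is the within-group primary test. It would go too far to infer that the dose comparison is biased in the same way: the ANCOVA compares randomized groups and adjusts for baseline HbA1c, so drift should largely balance. Nor do the documents show that any observed HbA1c fall is an artefact of the anchor.

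**What to change.** In inclusion 4 and exclusions 3, 4 and 12, count back from the Visit 1 HbA1c sample instead of from enrolment. This reduces the drift without removing it, and leaves the sample size of 52 per group unchanged. The cost is the wording of four criteria, with some subjects screened up to 3 weeks later. Because this study has already been run, the wording change serves a later protocol.

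For the data in hand, repeat the primary HbA1c analysis in subjects with at least 12 stable weeks before the Visit 1 sample. This needs the metformin start or last dose-change date. The plan records prior anti-diabetic medication and asks explicitly for the date of diabetes diagnosis, but does not say that metformin dates were captured, so the analysis depends on their being available. It should be identified as post hoc in the clinical study report, as the section on deviations from the original statistical plan requires. Where the dates exist, the cost is one additional analysis.
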